### 9.3.1 Adverse Event Reporting Period

Investigators will seek information on adverse events at each patient contact. All adverse events, whether reported by the patient or noted by study personnel, will be recorded in the patient's medical records. Adverse events will then be reported on the Adverse Event eCRF as follows:

**From informed consent until the initiation of study drug**, only serious adverse events related to study procedures. Any other adverse events occurring in this period should be only recorded on the Medical History.

**After initiation of study drug**, all adverse events regardless of relationship to study drug, will be reported until 4 weeks after the last dose of study drug.

Instructions for reporting adverse events that occur after the adverse event reporting period are provided in Section 9.6.

### 9.3.2 Eliciting Adverse Event Information

Investigators are advised to use a consistent method of non-directive questioning to elicit adverse event information at all patient evaluation time-points. Some examples of non-directive questions are: "How have you felt since your last clinic visit?" or "Have you experienced any changes to your health since your last visit?"

### 9.3.3 Assessment of Severity of Adverse Events

The adverse event severity grading scale for the NCI CTCAE (v4.03) will be used to assess adverse event severity. Table 18 will be used for assessing severity for adverse events that are not specifically listed in the NCI CTCAE.

**Table 18** Adverse event severity grading scale

Grade	Severity
1	Mild; asymptomatic or mild symptoms; clinical or diagnostic observations only; or intervention not indicated.
2	Moderate; minimal, local, or non-invasive intervention indicated; or limiting age-appropriate instrumental activities of daily living a
3	Severe or medically significant, but not immediately life-threatening; hospitalisation or prolongation of hospitalisation indicated; disabling; or limiting self-care activities of daily living b,c,d
4	Life-threatening consequences or urgent intervention indicated e
5	Death related to AE e

Abbreviations: NCI CTCAE = National Cancer Institute Common Terminology Criteria for Adverse Events.

Based on the NCI CTCAE (v4.03), which can be found at:

[https://evs.nci.nih.gov/ftp1/CTCAE/CTCAE\\_4.03/CTCAE\\_4.03\\_2010-06-14\\_QuickReference\\_8.5x11.pdf](https://evs.nci.nih.gov/ftp1/CTCAE/CTCAE_4.03/CTCAE_4.03_2010-06-14_QuickReference_8.5x11.pdf)

a Instrumental activities of daily living refer to preparing meals, shopping for groceries or clothes, using the telephone, managing money, etc.

b Examples of self-care activities of daily living include bathing, dressing and undressing, feeding one's self, using the toilet, and taking medications, as performed by patients who are not bedridden.

c If an event is assessed as a "significant medical event," it must be reported as a serious adverse event (Section 9.4.2 for reporting instructions), per the definition of a serious adverse event in Section 9.1.2.

d Grade  $\geq 2$  skin or subcutaneous, pharyngeal/laryngeal or mucosal reaction, clinically relevant retinal abnormalities detected by OCT should be reported as Adverse Events of Special Interest, as indicated in Section 9.1.3.

e Grade 4 and Grade 5 events must be reported as serious adverse events (Section 9.4.2 for reporting instructions), per the definition of serious adverse events in Section 9.1.2.

### 9.3.4 Assessment of Causality of Adverse Events

Investigators should use their knowledge of the patient, the information about the investigational drug and its non-clinical effects described in the Investigator Brochure, the circumstances surrounding the event, and an evaluation of any potential alternative causes to determine whether or not an adverse event is considered to be related to the study drug, indicating "yes" or "no" accordingly. The following guidance should be taken into consideration:

- Temporal relationship of event onset to the initiation of study drug.
- Course of the event, considering especially the effects of dose reduction, discontinuation of study drug, or reintroduction of study drug.
- Known association of the event with the study drug or with similar treatments.
- Known association of the event with the disease under study.

- Presence of risk factors in the patient or use of concomitant medications known to increase the occurrence of the event.
- Presence of non-treatment-related factors that are known to be associated with the occurrence of the event.

### **9.3.5 Procedures for Recording Adverse Events**

Investigators should use correct medical terminology/concepts when recording adverse events on the Adverse Event eCRF. Avoid colloquialisms and abbreviations.

Only one adverse event term should be recorded in the event field on the Adverse Event eCRF.

#### **9.3.5.1 Diagnosis versus Signs and Symptoms**

For adverse events, a diagnosis (if known) should be recorded on the Adverse Event eCRF rather than individual signs and symptoms (e.g., record only liver failure or hepatitis rather than jaundice, asterixis, and elevated transaminases). However, if a constellation of signs and/or symptoms cannot be medically characterised as a single diagnosis or syndrome at the time of reporting, each individual event should be recorded on the Adverse Event eCRF. If a diagnosis is subsequently established, all previously reported adverse events based on signs and symptoms should be nullified and replaced by one adverse event report based on the single diagnosis, with a starting date that corresponds to the starting date of the first symptom of the eventual diagnosis.

#### **9.3.5.2 Adverse Events Occurring Secondary to Other Events**

In general, adverse events occurring secondary to other events (e.g., cascade events or clinical sequelae) should be identified by their primary cause, with the exception of severe or serious secondary events. However, medically significant adverse events occurring secondary to an initiating event that are separated in time should be recorded as independent events on the Adverse Event eCRF. For example:

- If vomiting results in mild dehydration with no additional treatment in a healthy adult, only vomiting should be reported on the eCRF.
- If vomiting results in severe dehydration, both events should be reported separately on the eCRF.
- If a severe GI haemorrhage leads to renal failure, both events should be reported separately on the eCRF.
- If dizziness leads to a fall and subsequent fracture, all three events should be reported separately on the eCRF.

All adverse events should be recorded separately on the Adverse Event eCRF if it is unclear as to whether the events are associated.

### **9.3.5.3 Reporting of Progression of Disease**

Progression of the underlying malignancy should not be captured as an (S)AE (including fatal AEs). Clinical symptoms may be reported as AEs, if the symptom cannot be determined as exclusively due to the progression of the underlying disease or does not fit the expected pattern of progression for the disease under study. If a new malignancy appears, it will be considered an AE.

### **9.3.5.4 Persistent or Recurrent Adverse Events**

A persistent adverse event is one that extends continuously, without resolution, between patient evaluation time-points. If the initial severity of a persistent adverse event worsens, the entry in the Adverse Event eCRF should be marked as resolved and a new separated entry with the worsening severity should be added. If the event becomes serious, the Adverse Event eCRF should be updated to reflect this.

A recurrent adverse event is one that resolves between patient evaluation time-points and subsequently recurs. Each recurrence of an adverse event should be recorded separately on the Adverse Event eCRF.

### **9.3.5.5 Abnormal Laboratory Values**

Not every laboratory abnormality qualifies as an adverse event. A laboratory test result should be reported as an adverse event if it meets any of the following criteria:

- Accompanied by clinical symptoms.
- Results in a change in study treatment (e.g., dosage modification, treatment interruption, or treatment discontinuation).
- Results in a medical intervention (e.g., potassium supplementation for hypokalaemia) or a change in concomitant therapy.
- Clinically significant in the Investigator's judgment.

Medical and scientific judgment should be exercised in deciding whether an isolated laboratory abnormality should be classified as an adverse event.

### **9.3.5.6 Abnormal Vital Sign Values**

Not every vital sign abnormality qualifies as an adverse event. A vital sign result should be reported as an adverse event if it meets any of the following criteria:

- Accompanied by clinical symptoms.
- Results in a change in study treatment (e.g., dosage modification, treatment interruption, or treatment discontinuation).
- Results in a medical intervention or a change in concomitant therapy.
- Clinically significant in the Investigator's judgment.

Medical and scientific judgment should be exercised in deciding whether an isolated vital sign abnormality should be classified as an adverse event.

### **9.3.5.7 Abnormal Liver Function Tests**

The finding of an elevated ALT or AST ( $> 3 \times \text{ULN}$ ) in combination with either an elevated total bilirubin ( $> 2 \times \text{ULN}$ ) or clinical jaundice in the absence of cholestasis or other causes of hyperbilirubinaemia is considered to be an indicator of severe liver injury (Hy's Law). Therefore, Investigators must report as a serious adverse event the occurrence of either of the following:

- Treatment-emergent ALT or AST  $> 3 \times \text{ULN}$  in combination with total bilirubin  $> 2 \times \text{ULN}$  (Hy's Law). In the event of suspected Hy's Law CB-103 administration has to be put on hold immediately and permanent discontinuation of treatment should be considered.
- Treatment-emergent ALT or AST  $> 3 \times \text{ULN}$  in combination with clinical jaundice.

The most appropriate diagnosis or (if a diagnosis cannot be established) the abnormal laboratory values should be recorded on the Adverse Event eCRF (see Section 9.3.5.1) and reported to the Sponsor immediately (i.e., no more than 24 hours after becoming aware of the event) as a serious adverse event (see Section 9.4.2).

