## DOSE-LIMITING TOXICITY (DLT)

DLT is defined as an adverse event or abnormal laboratory value assessed as unrelated to disease progression, inter-current illness, or concomitant medications, that occurs  $\leq$  28 days following the first dose of CB-103 (Cycle 1) and that meets any of the following criteria shown in the table below.

**Note:** For T-ALL/T-LBL patients enrolled into the confirmatory cohort of Part A or expansion cohort of Part B of the study, haematological toxicity in non-responding patients, or death after progression should not be considered as DLT.

Toxicity	Any of the following criteria
Haematology	$\geq$ CTCAE grade 3 neutropenia (ANC $<$ $1.0 \times 10^9/L$ ) lasting for $\geq$ 7 days 
	$\geq$ CTCAE grade 4 neutropenia (ANC $<$ $0.5 \times 10^9/L$ ) 
	Febrile neutropenia (ANC $<$ $1.0 \times 10^9/L$ , fever $\geq$ $38.3^\circ C$ ) 
	CTCAE grade 3 thrombocytopenia (platelets $<$ $50-25 \times 10^9/L$ ) lasting for $\geq$ 7 days and/or with signs of bleeding 
	CTCAE grade 4 thrombocytopenia (platelets $<$ $25 \times 10^9/L$ ) 
	$\geq$ CTCAE grade 4 anaemia 
Cardiac	$\geq$ CTCAE grade 3
	$\geq$ CTCAE grade 3 hypertension for $>$ 14 consecutive days despite optimal anti-hypertension therapy
Renal	Serum creatinine $>$ 2 x ULN
Hepatic	$\geq$ CTCAE grade 3 total bilirubin ( $>$ 3 x ULN)
	CTCAE grade 2 total bilirubin lasting for $\geq$ 7 days.
	$\geq$ CTCAE grade 2 total bilirubin and $\geq$ CTCAE grade 2 ALT or AST
	CTCAE grade 3 ALT or AST lasting for $\geq$ 7 days
	CTCAE grade 4 ALT or AST
	Hepatic lab parameters fulfilling Hy's Law: AST/ALT 3 x ULN and concomitant 2 x ULN for bilirubin 
Pancreatic	$\geq$ CTCAE grade 3 pancreatitis
	CTCAE grade 3 asymptomatic serum lipase lasting for $\geq$ 7 days
	CTCAE grade 3 symptomatic serum lipase
	CTCAE grade 4 serum lipase
Other adverse events	Any CTCAE grade 5 toxicity
	$\geq$ CTCAE grade 3 blurred vision or any other eye disorder
	$\geq$ CTCAE grade 3 vomiting or nausea for $\geq$ 72 hours despite optimal anti-emetic therapy 
	$\geq$ CTCAE grade 3 diarrhoea for $\geq$ 72 hours despite optimal anti-diarrhoea treatment 

CONFIDENTIAL

May not be used, divulged, published, or otherwise disclosed without the consent of Cellestia Biotech AG

	Any other ≥ CTCAE grade 3 adverse event, except for the exclusions noted below

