	Inability to administer CB-103 on ≥ 75% of scheduled treatment days during cycle 1 (i.e., ≥ 21 days for a 28-day daily dosing schedule) due to unresolved adverse event of any grade related to CB-103.
	Delay in 2 nd cycle administration due to failure of recovery from a possibly, probably or definitely related adverse event to grade ≤ 1 or baseline by Day 43 (D28 of cycle 1 + 15 days), except for alopecia.
Exceptions to DLT criteria	CTCAE grade 3 or 4 elevations in alkaline phosphatase
	< 96 hours of CTCAE grade 3 fatigue
	Investigations (e.g., laboratory values) CTCAE grade ≥ 3 which are judged not clinically significant by the Investigator 

Abbreviations: ALT, alanine aminotransferase; ANC, absolute neutrophil count; AST, aspartate aminotransferase; CTCAE, Common Terminology Criteria for Adverse Events; DLT, dose-limiting toxicity; PRBC, packed red blood cells; ULN, upper limit of normal.

NCI CTCAE v4.03 will be used for all grading.

 Patients may receive supportive care (e.g. use of granulocyte-colony stimulating factor [G-CSF], packed red blood cells (PRBCs), platelets) as per local institutional guidelines. However, during the DLT period it is not allowed to administer these supportive measures prophylactically.

 Patients fulfilling the criteria for Hy's law will need to be immediately discontinued from treatment

 Optimal therapy for vomiting or diarrhoea will be based on institutional guidelines and based on Section 7.4.7, with consideration of the prohibited medications listed in the protocol.

 An abnormal lab value / investigation should be deemed clinically significant (assessed by the Investigator) if either of the following conditions is met:

- The abnormality suggests a disease and/or organ toxicity that is new or has worsened from baseline
- The abnormality is of a degree that requires additional active management, e.g., change of dose, discontinuation of the drug, close observation, more frequent follow-up assessments, or further diagnostic investigation.

Therefore, a clinically significant lab value is one that indicates a new disease process, an exacerbation or worsening of an existing condition, or requires further action(s) to be taken.

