#### **7.4.5 Dose Modifications, Dose Delays and Treatment Discontinuation**

Every effort should be made to administer CB-103 at the planned dose and schedule. In the event of treatment-related toxicities and DLT with CB-103, dose or schedule adjustments are required and have to be undertaken by the Investigator in the best interest of the patient to continue therapy. In the event of multiple toxicities, the dose modification should be based on the worst toxicity observed (according to the NCI CTCAE, v4.03). Any adjustment to the CB-103 dose should be documented in the eCRF.

Dose adjustments and interruptions criteria are described in the following sections. Depending on the type, severity and timing of the events, the Investigator will determine and decide on dose reductions and resumption of treatment. The following rules have to be followed:

- After Cycle 1 / Day 1, a continuous treatment interruption of more than 14 days will result in discontinuation of the patient from the study. Interruption of treatment not related to CB-103 may not require discontinuation; in such a case treatment continuation must be discussed with the Sponsor.
- Patients with a continuous treatment delay for more than 7 days during cycle 1 in Part A of the study (DLT period) that is not due to a drug-related AE, will be considered non-evaluable for DLT and will need to be replaced accordingly.
- Doses of CB-103 held or missed will not be made up (i.e., cycles will not be prolonged beyond the 28th calendar day in order to make up any missed doses).
- If doses of CB-103 are missed or forgotten to be taken for more than three sequential dosing events and if this happens more than once, this will result in discontinuation of the patient from the study. Dose delays as outlined above to recover from adverse events are allowed.
- If a treatment interruption continues beyond Day 28 of the current cycle, then the day when treatment is restarted will be counted as Day 1 of the next cycle.
- During cycle 1 in Part A (DLT period), any dose adjustments must be discussed with and approved by the Sponsor.
- One dose reduction is allowed per patient. In case the patient shows clinical benefit a 2nd dose reduction might be allowed, but this needs to be agreed upon on a case-by-case basis with the Sponsor. Section [7.4.6.1](#) describes the CB-103 dose modifications for the haematologic and non-haematologic toxicities not clearly attributed to disease.

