#### **7.4.6.1.3 Hepatic Toxicities**

If bilirubin ≥ CTCAE grade 2 or AST/ALT ≥ CTCAE grade 3 has been demonstrated, these parameters must be repeated at least twice a week until resolution to ≤ CTCAE grade 1 (or baseline if liver metastases were present at baseline), to allow for initiation of re-treatment and then at least weekly until either resolution or until stabilisation.

Patients with total bilirubin > ULN (any duration) should have fractionation of bilirubin into total/direct or indirect/direct components and any additional work-up as clinically indicated by these results. Follow-up of hyperbilirubinaemia should proceed as per the guidelines above, irrespective of the results of fractionation.

**Table 6** Dose modifications for hepatic toxicities

Dose Modifications for CB-103	
Worst Toxicity CTCAE Grade unless otherwise specified (Value)	At any time during a cycle of CB-103 (including intended day of dosing)
Hepatic toxicities:	
Bilirubin	
Grade 1 (< 1.5 x ULN)	Maintain dose level
Grade 2 (1.5 - 3 x ULN)	Omit dose administration until resolved to ≤ grade 1, 
 
• If resolved in ≤ 7 days, then maintain dose level
 
• If resolved in > 7 days, then ↓ 1 dose level
 

Grade 3 (> 3.0 - 10.0 x ULN)	Omit dose administration until resolved to ≤ grade 1, then ↓ 1 dose level
Grade 4 (> 10.0 x ULN)	Omit dose administration and discontinue patient from study treatment
AST or ALT	
Grade 1 (> ULN – 3.0 x ULN) & Grade 2 (>3.0 - 5.0 x ULN) without increase in total bilirubin >2 x ULN	Maintain dose level
Grade 3 (> 5.0 - 20.0 x ULN) without increase in total bilirubin >2 x ULN	Omit dose administration until resolved to ≤ grade 1 (or ≤ grade 2 in case of liver metastasis), then 
 
• If resolved in ≤ 7 days, then maintain dose level
 
• If resolved in > 7 days, then ↓ 1 dose level
 

Grade 4 (> 20.0 x ULN) without increase in total bilirubin >2 x ULN	Omit dose administration until resolved to ≤ grade 1, then ↓ 1 dose level

 Common Terminology Criteria for Adverse Events (CTCAE Version 4.03)

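### After Cycle 1 the protocol gives no single rule on restarting CB-103 when AST or ALT exceeds 3 x ULN with bilirubin above 2 x ULN

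*Protocol*

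**What the plan says.** Three places in the protocol deal with this liver pattern.

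- **Synopsis, Dose-Limiting Toxicity, footnote 2.** Patients who fulfil Hy's "law will need to be immediately discontinued from treatment". The footnote belongs to a DLT criterion that applies to the first 28 days, and a DLT must be "assessed as unrelated to disease progression, inter-current illness, or concomitant medications".
- **Section 9.3.5.7.** The pattern is called an indicator of severe liver injury "in the absence of cholestasis or other causes of hyperbilirubinaemia", and it is reported as an SAE. The instruction is: "In the event of suspected Hy's Law CB-103 administration has to be put on hold immediately and permanent discontinuation of treatment should be considered". No cycle limit and no restart condition are given. AST or ALT above 3 x ULN with clinical jaundice is a second SAE trigger.
- **Section 7.4.6.1.3 and Table 6.** Every AST/ALT row is limited to cases without bilirubin above 2 x ULN, for example "Grade 4 (> 20.0 x ULN) without increase in total bilirubin >2 x ULN". The bilirubin rows do not mention AST or ALT. At Grade 2, after a hold, the row reads "If resolved in ≤ 7 days, then maintain dose level", with one level lower if recovery takes longer. Grade 3 restarts one level lower. Grade 4 discontinues. The text before the table has both parameters followed until Grade 1 or lower ("or baseline if liver metastases were present at baseline), to allow for initiation of re-treatment").

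The synopsis sends toxicities in the confirmatory cohort and Part B to Section 7.4.6. Section 7.4.6.1 applies during and after Cycle 1 in Part A and throughout Part B.

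**The concern.** A site that meets this pattern after Cycle 1 can find three answers on restart: stop, hold and consider stopping, or hold and resume. The table that sites are told to use for dosing is the one without the row. A patient with probable severe drug-induced liver injury could therefore be rechallenged, and identical cases could be handled differently across sites.

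The liver is not a theoretical concern here. Section 2.5.6 reports one SAE related to CB-103, a drug-induced liver injury in a patient with extensive liver involvement, and Section 2.5.4 names the liver as a target organ in rats and dogs. About 45 confirmatory-cohort and 100-140 Part B patients are planned. Part B treatment runs for up to 12 cycles, so most exposure of patients who stay on treatment falls after Cycle 1.

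**Working it through.** There is no planned figure to reproduce. The check sets the rules side by side for AST or ALT above 3 x ULN with bilirubin above 2 x ULN.

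**Step 1: Cycle 1.** Footnote 2 requires discontinuation, and Section 9.2.4 withdraws a patient who has a DLT. Both point the same way, so Cycle 1 is settled for events that qualify as DLTs.

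**Step 2: after Cycle 1, Table 6 by bilirubin level (AST/ALT above 3 x ULN throughout).** No AST/ALT row applies at onset, because each excludes bilirubin above 2 x ULN. The bilirubin rows then give:

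- above 2 and up to 3 x ULN (Grade 2): hold to Grade 1 or lower, then same dose if this takes 7 days or less, one level lower if longer;
- above 3 and up to 10 x ULN (Grade 3): hold, then one level lower;
- above 10 x ULN (Grade 4): discontinue.

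The gap is therefore bilirubin above 2 and up to 10 x ULN.

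**Step 3: a worked case.** Cycle 3, ALT 4 x ULN (Grade 2) and bilirubin 2.5 x ULN (Grade 2), both at Grade 1 or lower within 7 days.

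- Section 9.3.5.7: hold, and consider permanent discontinuation.
- Table 6: resume at the same dose. Once bilirubin has fallen, the AST/ALT rows apply again, and a Grade 1 ALT also maintains the dose.
- Footnote 2, if read beyond Cycle 1: stop.

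**Step 4: do the general rules in Section 7.4.5 decide the case?**

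- "In the event of multiple toxicities, the dose modification should be based on the worst toxicity observed": taken singly, both values are Grade 2, which leads back to the Grade 2 bilirubin row.
- The most-conservative-approach rule covers a haematological toxicity together with a non-haematological one, not two hepatic values.
- An interruption of more than 14 days leads to discontinuation. A 7-day hold is inside that limit.
- Resumption is otherwise the investigator's decision. SAP 2.1.4 only refers back to Section 7.4.5.

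None of these supplies a restart rule.

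**Step 5: analysis.** The dose-determining set and the BLRM use Cycle 1 DLTs. A restart decision after Cycle 1 changes neither.

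**The case against.** The strongest reply is that the AST/ALT rows stop exactly at the Hy's law bilirubin threshold, so the combined case is meant to leave Table 6 for the specific text: hold when Hy's law is suspected (Section 9.3.5.7), discontinue when it is fulfilled (footnote 2). The exclusion of cholestasis and other causes, and the attribution condition in the DLT definition, fit that reading. It is sensible, but nowhere written as a rule, and the bilirubin rows carry no matching exclusion.

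It can also be said that the DLT concept reaches past Cycle 1. The synopsis has a DLT note for T-ALL/T-LBL patients in the confirmatory cohort and Part B, Section 7.4.4 says only that first-cycle DLTs are necessarily used for escalation, and Table 8 calls QTcF of 500 ms or more during study treatment a DLT. The formal definition remains 28 days. If footnote 2 did run further, it would conflict directly with Section 9.3.5.7 and with the bilirubin restart rows, so alignment would still be needed.

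The safeguards are real: SAE reporting within 24 hours, possible independent medical assessment by the Sponsor, CRC review of SAEs at least quarterly, withdrawal for unacceptable adverse events, and the 14-day limit. They reduce the chance of an unwise rechallenge without deciding restart.

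A reader might also infer that Table 6 treats the combined case more leniently than raised ALT alone, for instance that ALT 25 with bilirubin 2.5 x ULN could resume at the same dose once bilirubin recovers. The documents do not support that. The text before Table 6 requires both parameters to recover, and once bilirubin is back to Grade 1 the AST/ALT rows apply again: ALT still above 20 x ULN means hold and then one level lower, and ALT above 5 and up to 20 x ULN means a continued hold.

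**Conclusion.** The inconsistency holds and should be corrected. It concerns restart only, after Cycle 1, for AST or ALT above 3 x ULN with bilirubin above 2 and up to 10 x ULN. The 14-day limit narrows it in practice to events that resolve within 14 days, apart from interruptions unrelated to CB-103, where Section 7.4.5 leaves continuation to discussion with the Sponsor. How often such events would occur cannot be estimated from the documents.

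The conclusion rests on reading footnote 2 within the 28-day DLT definition to which it is attached. On the wider reading the three places contradict each other outright, and the remedy is the same. A reader might infer that dosing could continue through such an event, or that the dose-finding results are at risk. Neither follows: every applicable rule interrupts dosing at once, and the DLT counts, dose-determining set and BLRM input are untouched.

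**What to change.** Add one row to Table 6, and align footnote 2 and Section 9.3.5.7 to it:

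*Treatment-emergent AST or ALT >3 x ULN with total bilirubin >2 x ULN or clinical jaundice (any cycle, Parts A and B): hold CB-103 immediately; discontinue permanently unless an alternative cause (e.g. cholestasis or disease progression) is documented. The Grade 2 and 3 bilirubin restart rules do not apply; the Grade 4 bilirubin row stays in force.*

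Leave the other rows as they are, so that bilirubin of 1.5 to 2 x ULN with raised AST/ALT still leads to a hold.

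Do not replace the 3 x ULN trigger with a multiple of baseline for patients with liver metastases, who may enter with AST/ALT up to 5 x ULN (Section 6.1.1, criterion 3c). Suppose, as an assumption, a trigger of 2 x baseline: for baseline ALT of 5 x ULN it becomes 2 x 5 = 10 x ULN. A patient at ALT 9 and bilirubin 2.5 x ULN would then miss the new row and fall back to the Grade 2 restart row, although Section 9.3.5.7 requires a hold today. The alternative-cause clause covers these patients. Entry bilirubin is at most 1.5 x ULN, so a value above 2 x ULN is always a rise on study.

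The cost is wording in three places, with no change to visits, sample size or analysis. The downside is that a few patients lose the option of rechallenge.
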